7.3. Adverse Events and Risks

Overall, setmelanotide has been generally well-tolerated in previous studies. Drug-Related TEAEs (for which the adverse event was assessed as possibly or probably related to study drug by the investigator) were reported. Because very few studies have been done using setmelanotide, there may be other unknown side effects. The PIs (or a covering clinician) will be available at all times to study participants in the event of a clinical emergency; both this availability and how to reach the investigators in an emergency will be clearly communicated orally and in writing to study participants. All study interventions will be provided free of cost.

Please refer to the current Investigator's Brochure for a comprehensive summary of the AEs reported to date.

7.3.1. Medical monitoring

The medical monitoring for the study may be delegated to a medical monitor supplied by the CRO managing the operational conduct of this study. The PI has overall responsibility for the integrity of the study and participant safety. This information, as well as any other unanticipated problems involving risks to patients or others, will also be reported to the FDA.

This study will also be monitored by a safety monitoring committee, who will be responsible for careful safety evaluations of patients, while treatment continues in this study.

During the conduct of study, responsibilities of the SMB will be to review periodically the study data by performing a qualitative and quantitative safety assessment. In addition, the SMB should determine whether the basic study assumptions remain valid, and evaluate whether the overall integrity, scientific merit and conduct of the study are still acceptable. The SMB will make decisions regarding continuation or termination of the study or suggest changes in the design of the study or its procedures or both.

The SMB members will be comprised of both internal Rhythm employees (i.e. Rhythm's CMO) and persons independent of Rhythm. The SMB will meet quarterly throughout the duration of the trial.

7.4. Monitoring of Adverse Events and Period of Observation

AEs will be recorded on the CRFs starting from Screening up to and including the Final Study Visit. SAEs and deaths will be recorded on the CRFs starting from the time the ICF is signed and continuing through the Final Study Visit. All AEs should be monitored until they are resolved or are clearly determined to be due to a patient's stable or chronic condition or intercurrent illness(es).

Any SAE that occurs at any time after completion of the study, which the investigator considers to be related to study drug, must be reported to Rhythm or designee.

7.5. Guidelines for Additional Monitoring and Suspension of Dosing for a Patient

Patients will be monitored carefully during the treatment period during on site clinic visits as well as periodic telephone calls made to the patients by the study staff. In the event a patient is withdrawn from treatment due to an AE, the patient should be encouraged to complete the final study/early termination visit to monitor the event to resolution and obtain additional protocol defined safety assessments.

Specific guidelines for dermatological events, elevated liver function tests (LFTs), and penile erections are provided in the [Appendices](#). At all times, this guidance is subject to the clinical judgment of the Investigator and study consultants (if applicable).

The Investigator shall notify the Medical Monitor in the event any study participant fulfills any of the criteria defined in the appendices noted above, or undergoes additional monitoring for any of the events defined herein.

7.5.1. Depression or Suicidality

A patient should be referred to a MHP if he/she has:

- A [REDACTED].
- Any suicidal behavior.
- Any [REDACTED].

A referral to a MHP should also be made if in the opinion of the Investigator it is necessary for the safety of the patient. If a patient's psychiatric disorder can be adequately treated with psycho- and/or pharmacotherapy, then the patient, at the discretion of the MHP, should be continued in the trial.

8. STATISTICAL PROCEDURES

This section describes the plans for analysis. Details on the statistical plan will be provided in a complete Statistical Analysis Plan (SAP). Any additional analyses and specific conventions for analysis will be described in the SAP and Clinical Study Report (CSR).

8.1. Sample Size Estimation and Primary Power Statement

The primary endpoint is proportion of patients in the FAS who demonstrate at least 10% weight at 1 year (10-14months post baseline) compared to baseline. Patients with missing data after 10 months from baseline will be counted as not having 10% weight loss at 1 year. The primary research hypothesis is that this proportion is at least 5%. The null hypothesis is that this proportion is at most 5%. Rationale for the 5% historical control value for this comparison is as follows.

The available data suggests that 0% of LEPR deficiency patients would demonstrate at least 10% weight loss in a single year, even with extraordinary measures. The exception might be after bariatric surgery, as some patients have had very short-term improvements, though over time their overwhelming hunger leads to weight regain. In the absence of such measures in our clinical trial (exclusions from the trial), and the general contraindication of bariatric surgery in this population, it is defensible to consider that no (0%) patients would meet these criteria and the statistical comparison for this endpoint should be a comparison to a 0% proportion. Despite this strong rationale based on the natural history of these patients, since the data are limited and the number of patients in the trial is small, it is probably more appropriate to go beyond this very conservative estimate of 0% responders, to do our historical control comparisons assuming that a small proportion of the population (i.e. 5%, or a null of 0.05) *might* show a 10% weight loss in any given calendar year; hence we propose a categorical comparison to a 5% responder estimate in untreated historical patients.

The following power table shows the power to detect various proportions who achieve 10% weight loss at 1 year for LEPR patients, assuming a null hypothesis value of 5% responders for alpha = 0.05, 1-sided:

True Underlying Proportion	Power to Reject Null Hypothesis and Conclude True Proportion is Higher
0.2	0.322
0.3	0.617
0.4	0.833
0.5	0.945
0.6	0.988
0.7	0.998
0.8	>0.999
0.9	>0.999

8.2. Statistical Methods

Statistical methods, populations and approaches to address multiplicity of secondary endpoints and missing data will be outlined in the SAP.

The primary analysis will be conducted based on a Full Analysis Set (FAS), which is defined as all subjects who received at least 1 dose of study medication and have a baseline measurement (regardless of whether at least one post-baseline efficacy assessment is observed). All available measurements (including data from patients who discontinue active treatment) will be included in the analysis. The comparison of post-treatment values versus baseline and of proportions to null hypothesis values will be carried out via 1-sided statistical test at an alpha=0.05. No adjustment for multiplicity is needed for the single primary endpoint (i.e. percent of patients who achieve at least 10% weight loss after 1 year of treatment versus the null hypothesis value of 0.05).

For the primary endpoint, and all other endpoints, the last value obtained prior to the first dose of active treatment will be considered the baseline value for statistical analyses.

As this patient population is extremely rare, all data collected, even if outside of visit windows, will be included in all analyses of endpoints.

AEs will be coded by using the most current version of Medical Dictionary for Regulatory Activities (MedDRA) and summarized by system organ class, preferred term, and treatment group for the number and percent of AEs reported, the number of patients reporting each AE, and the number of patients with any AE.

A by-patient AE data listing including onset and resolution dates, verbatim term, preferred term, treatment, severity, relationship to treatment, action taken, and outcome will be provided.

Safety data including laboratory evaluations and vital signs assessments will be summarized by time of collection and by treatment group. In addition, change from baseline to any post-dose values will be summarized for vital signs and clinical laboratory results. Frequency of patients with abnormal safety laboratory results will be tabulated by treatment.

Plasma concentrations will be summarized. Plasma concentrations may be compared to PD endpoints.

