2.2. Study Endpoints

The primary endpoint is the proportion of patients in the full analysis set (FAS) who meet the $\geq 10\%$ weight loss threshold (responders) after ~ 1 year of treatment, compared to the proportion from historical data (at most 5% responders in the null population)

Supporting secondary, [REDACTED] endpoints include:

The safety and tolerability of setmelanotide QD SC injection will be assessed by the frequency and severity of AEs as well as changes in physical examinations, electrocardiograms (ECGs), vital signs (including resting BP and HR), laboratory evaluations, monitoring for changes in [REDACTED] in patients ≤ 16 years of age and injection site reactions.

Hunger will be assessed daily throughout the study. Patients ≥ 12 years of age will self-report their hunger by responding to three questions asking about their hunger at its worst, hunger in the morning (prior to dosing), and hunger on average in the previous 24 hours using [REDACTED]

[REDACTED]

Two global hunger questions will also be administered to assess patients' perceptions of their current status and change from baseline at key timepoints, including the Patient Global Impression of Severity (PGIS) and Patient Global Impression of Change (PGIC) for those ≥ 12 years of age. [REDACTED]

[REDACTED]

Body composition assessments including total body weight loss, fat loss, and [REDACTED] measured in kg as well as percent change from baseline at the end of 1 year of treatment.

Glucose parameters as measured by fasting glucose, HbA1c and OGTT with focus on parameters of insulin sensitivity over time will be assessed. OGTT will not be performed for subjects with a diagnosis of Type 1 or Type 2 diabetes.

[figure not shown]
Waist circumference will be measured per US National Heart Lung and Blood Institute criteria [2000 NHLBI] over time.

To ensure improvements in weight and hunger are drug related in this ultra-rare patient population, a varying double-blind placebo withdrawal period will be implemented that will allow each patient to serve as their own control. Weight and hunger will be measured during this period to assess the efficacy of stopping and restarting setmelanotide treatment.

Potential improvements in [REDACTED] will be assessed over time.

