3. INVESTIGATIONAL PLAN

3.1. Overall Design and Plan of the Study

This is a pivotal Phase 3 study to assess long-term (1 year) efficacy of setmelanotide in LEPR deficiency obesity.

After providing informed consent, patients will enter the Screening Period. During the Screening Period, patients will be assessed for eligibility and instructed to complete a hunger questionnaire daily for a minimum of one week and ideally two weeks to establish a baseline and to enhance the understanding of hunger symptoms associated with LEPR deficiency obesity prior to treatment with setmelanotide. As LEPR deficiency is ultra-rare, obtaining daily hunger scores as well as a very detailed medical history (medical record review) during Screening will allow for the collection of important patient specific data (see Appendix 11.3; e.g., growth and weight curves, other associated [REDACTED] abnormalities, pediatric developmental milestones or disturbances, and possible orthopedic or respiratory complications due to weight gain) that will allow for a better understanding of this rare monogenic form of obesity.

After the Screening Period, there are four treatment phases to the study:

Open Label Dose Titration Phase (2 – 12 weeks)

In this phase of the study, a patient's individual therapeutic dose will be established. The starting dose is 1.0 mg for adult patients and 0.5 mg for adolescent and 0.25 mg for pediatric patients.

Patients will return to the clinic every two weeks to assess their weight loss and hunger scores and dosing will increase every two weeks in 0.5 mg increments until a patient's individual therapeutic dose is established per the guidelines in Appendix 11.8.

As this is a global study, the maximum allowable dose differs across countries based on feedback from competent authorities. The US, UK and the Netherlands have approved a maximum dose of 3.0 mg, while Germany and France have approved a maximum dose of 2.5 mg. Therefore, the duration of the dose titration stage will range from 2 to 12 weeks, depending on the number of escalations required to define the therapeutic dose and the approved maximum dose in the country of the participating site.

Open Label Phase (10 weeks)

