5.5. Duration of Patient Participation

Individual patient participation in this study (Screening period [2-4 weeks], open label dose titration period [12 weeks maximum duration], open label active treatment [10 weeks], double-blind placebo-controlled withdrawal period [8 weeks], and open label treatment [32 weeks]) will range between a minimum of approximately 54 weeks and a maximum of approximately 66 weeks, as currently planned.

Patients who have had a positive response to setmelanotide after 1 year of treatment will have the opportunity to enroll in a future, separate, extension protocol to allow for continued treatment. This future extension protocol will be submitted and approved by applicable regulatory authorities prior to patients dosing beyond this protocol's study duration.

The end of the trial will be defined as the last patient last visit.

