Any patient withdrawing from the study will complete the Early Termination Visit, if possible, and will be encouraged to complete all remaining study visits. For those patients not willing to complete study visits at the clinic, home health care practitioner visits or telephone follow-up may be acceptable to obtain minimum patient self-reported data (i.e.: weight, AEs, etc.).

Detailed descriptions of the safety, PD and █ procedures to be conducted during this study are provided in the sections below. The amount of blood volume to be drawn for these procedures is within the acceptable limits for each visit and over the duration of the study (Appendix 11.12). However, blood draws may be challenging in this population of extremely obese patients due to poor access to their veins. In these instances, the PI should contact the Medical Monitor to prioritize sampling, with samples being collected for safety the highest priority.

Patients will be required to fast overnight on the day preceding all visits, beginning with the initial Screening Visit. Patients will be allowed to take their usual medications with a sip of water on the morning of each clinic visit.

The Screening Period can occur within ~ 4 weeks of Day 1 and should be scheduled within this timeframe to allow test results to be received and continued eligibility of patients confirmed prior to the first dose on Day 1. Assessments may occur over multiple days during the Screening Period. All screening bloodwork should be collected between Study Day -28 and -14 in order to ensure the WHO maximum cumulative blood volumes are not exceeded over the course of the study. To obtain sufficient baseline data on symptoms of hunger (collected daily), the screening period should be a minimum of two weeks and up to four weeks.

To provide flexibility to the patient and study staff for the number of clinic visits, the actual scheduling of clinic visits can allow flexibility in timing of visits. During the Dose Titration phase, the goal will be for visits to occur within +/- 3 days. But as this patient population is ultra-rare, all data collected, even if outside of visit windows, will be included in all analyses of endpoints.

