Global Hunger Questions: Two global questions will be asked at certain study visits per the Schedule of Assessments. For patients ≥ 12 years of age, the patient will answer the questions themselves.

[figure not shown]
Daily Hunger Questionnaire: Hunger will be assessed daily in all patients.

For patients ≥ 12 years of age, a set of three questions will be asked using [REDACTED]

The daily hunger questionnaire will be completed daily, prior to dosing in the morning. Patients will record their hunger scores prior to the morning meal (fasted).

The Global Hunger Questions and Daily Hunger Questionnaire is in Appendix 11.9.

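### Read literally, the all-endpoint baseline rule in Section 8.2 makes the hunger baseline a single diary entry, although weeks of daily scores are collected partly to establish it

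*Protocol*

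**What the plan says.** Protocol Section 8.2 gives a single baseline definition: "For the primary endpoint, and all other endpoints, the last value obtained prior to the first dose of active treatment will be considered the baseline". It makes no exception for diary measures. The same section says that "The comparison of post-treatment values versus baseline" is made with a 1-sided test at alpha 0.05.

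On hunger, the protocol says:

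- Section 2.1.2: hunger over one year in patients aged 12 and over is a secondary objective.
- Section 2.2: "Hunger will be assessed daily throughout the study".
- Section 6.4.15: "The daily hunger questionnaire will be completed daily, prior to dosing in the morning".
- Section 3.1: during screening, patients are to "complete a hunger questionnaire daily for a minimum of one week and ideally two weeks to establish a baseline" and to improve understanding of hunger symptoms before treatment.
- Section 6.1: "To obtain sufficient baseline data on symptoms of hunger (collected daily), the screening period should be a minimum of two weeks", and up to four. Section 5.5 also gives a screening period of 2 to 4 weeks.

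Section 8 defers detail: "Any additional analyses and specific conventions for analysis will be described in the SAP" and the clinical study report.

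**The concern.** A last-value rule suits measures taken once per visit, such as weight, waist or HbA1c. Applied to a diary completed every morning before dosing, it selects one day's entry per question. Sections 3.1 and 6.1 treat the screening scores as a body of baseline data whose length matters. If one entry were enough, no minimum length would be needed to establish the baseline.

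A single day carries the full day-to-day noise of the score into every patient's change from baseline. The trial plans about 10 patients, and fewer count for hunger if some are under 12, so avoidable noise is unwelcome. Leaving the definition open until open-label results have been seen would also leave a choice of baseline that is better fixed beforehand.

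**Working it through.** **The plan's own figures.** The only power figures in the protocol concern the primary responder endpoint. With N = 10, a null proportion of 5% and rejection at 3 or more responders, the exact binomial power at true proportions 0.2, 0.3, 0.4, 0.5, 0.6 and 0.7 is 0.3222, 0.6172, 0.8327, 0.9453, 0.9877 and 0.9984. This reproduces the table in Section 8.1. The exact type I error is 0.0115; a cut-off of 2 would give 0.0861. Nothing below changes these figures. The protocol gives no power, SD or correlation for hunger.

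**How much of the diary the rule uses.** One entry out of at least 7 (Section 3.1) or 14 to 28 (Section 6.1). The share left out of the baseline runs from 6/7 = 86% to 27/28 = 96%.

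**Effect on precision. The inputs are assumptions:**

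- s: within-patient day-to-day SD of the hunger score.
- tau: between-patient SD of the true change; t = tau/s, taken as 1, 2 and 3.
- rho: correlation of neighbouring days' deviations, first-order autoregressive; 0, 0.5, 0.7 and 0.9.
- Baseline and post-baseline days are far enough apart for their day-to-day errors to be independent.

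The variance of a 7-day mean relative to one day is

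v7 = [7 + 2 × Σ (7 − k) × rho^k, k = 1 to 6] / 49,

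which is 0.143, 0.348, 0.518 and 0.798 for the four values of rho.

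The SE of mean change with a one-day baseline, divided by that with a 7-day baseline, is:

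- post-baseline values as 7-day means: sqrt[(t² + 1 + v7) / (t² + 2·v7)]
- post-baseline values from a single day: sqrt[(t² + 2) / (t² + 1 + v7)]

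| Post-baseline value | t | rho 0 | rho 0.5 | rho 0.7 | rho 0.9 |
|---|---|---|---|---|---|
| 7-day mean | 1 | 1.29 | 1.18 | 1.11 | 1.04 |
| 7-day mean | 2 | 1.10 | 1.07 | 1.05 | 1.02 |
| 7-day mean | 3 | 1.05 | 1.03 | 1.02 | 1.01 |
| Single day | 1 | 1.18 | 1.13 | 1.09 | 1.04 |
| Single day | 2 | 1.08 | 1.06 | 1.04 | 1.02 |
| Single day | 3 | 1.04 | 1.03 | 1.02 | 1.01 |

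Three cells worked out, with 7-day post-baseline means:

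- Top (rho 0, t = 1): one-day baseline 1 + 1 + 0.143 = 2.143 s²; 7-day baseline 1 + 0.286 = 1.286 s². The ratio is sqrt(2.143/1.286) = 1.291, and the mean lowers the variance by 40.0%.
- Middle (rho 0.5, t = 2): 5.348 against 4.695 s², ratio 1.067, variance 12.2% lower.
- Bottom (rho 0.9, t = 3): 10.798 against 10.596 s², ratio 1.0095, variance 1.9% lower.

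Simulation of both post-baseline definitions over the same values of rho and t (400,000 patients per case) agrees within 0.002.

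**Incomplete diaries.** With only 4 consecutive completed days, the baseline error variance is 0.25, 0.52, 0.68 and 0.88 s² for the four values of rho, against 1.00 s² for one day. A 4-day minimum therefore still improves on a single entry.

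**The case against.** The strongest reply is that Section 8.2 says when baseline is taken, not how repeated entries form a value. Weight and height are measured in triplicate, and blood pressure is the average of three readings. Nobody would read the rule as taking only the third weighing, so a value may be a derived quantity, and for a diary that could be a weekly mean. Turning diary entries into an analysis value is ordinary SAP content, and Section 8 leaves specific conventions to the SAP, which is not shown. Parts of the hunger text are blacked out, and Appendices 11.8 and 11.9 are not in the copy reviewed. Section 6.1 also describes the screening diary in one place only as a way to understand hunger before treatment, and collecting more scores than enter a change score is not in itself a contradiction.

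Much of this limits the point without removing it. Triplicates are repeat readings at one timepoint; averaging across days is a different step, and no visible text extends the rule to it. The protocol is not silent here: it states a rule for every endpoint, and an SAP that used a weekly mean would have to depart from that sentence or rely on an unstated reading of it. What stands is that the intended meaning may already be a mean, that the redactions keep confidence low, and that the effect is modest. The top ratio of 1.29 needs uncorrelated days, t = 1, and a plan that averages seven days after baseline but uses one day before it; the protocol states no such mixed plan. With single-day values on both sides the maximum is 1.18.

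**Conclusion.** The point holds as a minor one, with low confidence about what the sponsor intended. As written, Section 8.2 reduces the hunger baseline to one day's entry, against the purpose that Sections 3.1 and 6.1 give to the screening diary.

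The consequence is a loss of precision in change from baseline for one secondary endpoint: an SE larger by about 1% to 29% under the assumed values, and by no more than 10% once tau is at least 2s. No eligibility criterion selects patients on hunger score, so there is no reason to expect bias. Within-patient contrasts in the withdrawal period need not use this baseline. Sections 3.1 and 6.1 are compatible with each other, since a two-week screening period satisfies both.

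**What to change.** Amend Section 8.2 so that, for the daily hunger items, baseline is the mean of the available scores in a fixed window before the first active dose. The last 7 days would fit the one-week minimum in Section 3.1. State a minimum number of completed days, for example 4, and a fallback for patients below it. Average post-baseline hunger over windows of the same length. Keep the last-value rule for measures taken once per visit.

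If a weekly mean was already intended, one clause in Section 8.2 saying so is enough. Sections 3.1 and 6.1 need no change.

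The cost is one or two sentences. The diary data are already collected, so patients carry no extra burden. The only small downside is that the completeness rule and the fallback must be set in advance.
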